**Cardiovascular Risk in People Older Than 55 Years and  
Cognitive Performance at 5 Years: an Estimation Model Based  
on Spanish Population. NEDICES-2-RISK study.**

NCT 03925844

Document Date: July 6, 2019

Dementia is unique in terms of prevalence, cost and impact. Any small advance in the prevention of dementia would benefit millions of people. Current data indicate that cardiovascular risk factors increase the risk of cognitive decline. The cardiovascular risk estimation by means of cardiovascular risk functions seems to be useful in the prediction of risk of cognitive deterioration. However, in the Spanish population, the incidence of coronary heart disease and stroke are lower than expected taking into account the cardiovascular risk factors.

The purpose of this study is to study the association between the cardiovascular risk of the study population, using the Framingham REGICOR and FRESCO cardiovascular risk functions, and the cognitive performance after 5 years of follow-up. The identification of individuals who have a high risk of cognitive decline in later years using predictive models of vascular risk would be a good approach to the prevention of cognitive impairment.

## **OBJECTIVES**

### **Primary**

The main objective is to evaluate the association between cardiovascular risk, calculated with the Framingham REGICOR and FRESCO risk functions, and the cognitive decline after 5 years of follow-up in the NEDICES-2-RISK cohort.

### **Secondary**

- (a) To describe the profile of patients according to their cardiovascular risk
- (b) To study the association between each cardiovascular risk factor in isolation and the cognitive decline after a 5-year follow-up
- (c) To study the association between calculated cardiovascular risk with the risk functions Framingham REGICOR and FRESCO and other non-neurological diseases
- (d) To analyze possible mediating effects between cardiovascular risk, cognitive decline and lifestyle
- (e) To investigate the effect of mediation of cognitive reserve indicators (verbal intelligence, education, occupation and lifestyle) on cognitive deterioration in different tests of the neuropsychological evaluation.

## **METHODS / DESIGN**

**Design.** Prospective longitudinal analytical observational study of cohort with 5 years of follow-up.

**Scope of study.** The scope of study is the Primary Care setting of the Spanish national health system.

**Study population.** The population of the NEDICES-2-RISK study are patients aged 55 to 74 who were included in the NEDICES-2 cohort (2014-2017), in which the presence of dementia in the initial neuropsychological evaluation was ruled out. The population of the NEDICES-2 study comes from the list of users with health cards of the participating doctors of the health centers

included and the sample selection was carried out by random sampling stratified by sex and age in groups of 5-year increase of people of 55 years and over.

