### Sample size

The sample size is 965 patients.

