### Procedure

Patients who agree to participate and sign the informed consent will undergo a neuropsychological assessment (after 5 years of follow-up) with the same test battery as in the first evaluation (performed between 2014-2017) by trained interviewers and The clinical variables (morbidity and cardiovascular risk factors) and treatment variables will be collected through a clinical interview.

Anthropometric variables, as well as chronic diseases and medication will be collected by the patient's doctor. The rest of the information will be collected by interviewers. See Table 1.

Table 1. Variables and measurements collected during the study

	Variables collected at baseline	Variables collected after 5 years of follow-up
Social and demographic variables collected by interviewers: - Age - Gender - Marital status - Education - Profession	X X X X X	X X
Health related variables collected by primary care physicians: - Blood pressure - Cholesterol levels - Weight and height - Morbidity - Pharmacotherapeutic treatment	X X X X X	X X X X X
Variables on lifestyle and health status collected by interviewers: - Alcohol consumption - Caffeine consumption - Tobacco use - Physical activity - Mediterranean diet - EuroQoL 5D-3L - Quality of life measurement scales	X X X X X X	X X X X X X
Neuropsychological assessment carried out by interviewers: - CES-D scale - Word accentuation test - MMSE 37 - Instrumental activities of daily living, Pfeffer scale	X X X	X X X

 
- Semantic Verbal Fluency test
 
- Six-Object Memory Recall Test
 
- Trail Making test
 
- Clock-drawing test
 
	X	X
Exposure variables calculated by the research team:		

 
- Framingham REGICOR function
 
- FRESCO function
 
	X	X
	X	X

CES-D scale: Center for Epidemiologic Studies Depression Scale; MMSE-37: Mini Mental State Examination 37 item-version; FRESCO: Función de Riesgo Española de acontecimientos Coronarios y Otros; REGICOR: Registre Gironí del Cor

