## STATISTICAL ANALYSIS

Initially, a review of the quality of the study data will be carried out: detection of errors in the coding, missing data and possible biases related to representativeness of the sample (for example, selection of subjects and loss in follow-up, among others).

Different descriptive statistics will be used to analyze the baseline characteristics (qualitative and quantitative variables) of the patients included in the study. For the categorical variables, such as the sociodemographic and clinical variables of the patients, they will be analyzed and represented by frequency tables (globally and by strata). For numerical variables, means and standard deviations will be calculated. Patients who leave the study will be described, including the characteristics of the patients and the reasons for the loss of follow-up.

The bivariate analysis will try to find the presence of a significant association between baseline cardiovascular risk and the score obtained in the cognitive and functional tests (MMSE 37, Trail Making Test, Semantic Verbal Fluency test, Six-Object Memory Recall Test, Clock drawing test, Pfeffer functional assessment scale). For this, the Pearson's Chi-square and Spearman statistical coefficients will be used, as appropriate.

Finally, multivariate analyses (multiple regression, analysis of covariance) will study the association between baseline cardiovascular risk (4 categories) and the psychometric and functional tests adjusted for relevant sociodemographic and clinical variables as potential confounding factors. Linear regression models of mixed effects (which take into account intrasubject variability when considering repeated measures) will be used, considering as a dependent variable the score obtained in each of the tests studied (one model for each scale) and as an independent, the cardiovascular risk basal (4 categories).

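### Patients are sampled from doctors' lists within health centres, but no model names a doctor or centre term; if risk and 5-year change both cluster, the standard errors are too small

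*Combined protocol and SAP*

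**What the plan says.** Under Methods / Design, the parent cohort "comes from the list of users with health cards of the participating doctors of the health centers". Patients were then drawn at random within sex and five-year age strata; neither doctor nor centre is named as a stratum.

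The Statistical Analysis section plans multiple regression, analysis of covariance and linear mixed models. The multivariate models are to be "adjusted for relevant sociodemographic and clinical variables as potential confounding factors", and the covariates are not listed. The mixed models are described as ones "which take into account intrasubject variability when considering repeated measures", "considering as a dependent variable the score obtained in each of the tests studied (one model for each scale". The exposure is baseline risk in four categories. No random or fixed effect for doctor or centre, no cluster-robust standard error and no related sensitivity analysis is mentioned. The opening data review covers coding errors, missing data and representativeness, but it adds no term to any model.

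The primary objective concerns "the cognitive decline after 5 years of follow-up in the NEDICES-2-RISK cohort". Table 1 separates the data collectors: "Health related variables collected by primary care physicians" include blood pressure and cholesterol, while the cognitive tests fall under "Neuropsychological assessment carried out by interviewers".

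**The concern.** Patients on one doctor's list, or in one health centre, may resemble each other in vascular risk and in cognitive change. A model that treats them as independent then overstates its precision. This is an observational association judged at p < 0.05 in one model per scale, so the error carries directly into what is called significant.

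A second issue is separate. If centres or doctors with higher-risk patients also show more decline for unrelated reasons, a model without cluster terms cannot separate that from an effect of risk. For patients with both assessments, a centre effect that is constant over time cancels from change, so for decline only differences in change matter. Where a model is fitted to score level, stable centre differences do not cancel. The plan names the score as the dependent variable.

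**Working it through.** **The plan's own figure.** "The sample size is 965 patients" comes with no effect size, SD, power, dropout or design effect, so it cannot be reproduced. It is used here only as n. Cluster sizes, ICCs, cluster-level correlations and category cut-points (quartiles) are all assumed. The 0.05 level is taken as two-sided.

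**Standard errors.** Risk is a patient-level variable, so the variance factor with m patients per cluster is

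DE = 1 + (m − 1) × ICC(risk) × ICC(change).

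The SE shortfall is 1 − 1/√DE, and the actual alpha is 2[1 − Φ(1.96/√DE)]. The grid takes m = 5, 10, 20, 40; ICC(change) = 0.02, 0.05, 0.10; ICC(risk) = 0.05, 0.10, 0.20 (36 combinations).

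- Smallest: 1 + 4 × 0.05 × 0.02 = 1.004; shortfall 0.2%, alpha 0.0505.
- Median: DE 1.062; shortfall 2.9%, alpha 0.057.
- Largest: 1 + 39 × 0.20 × 0.10 = 1.78; shortfall 25.0%, alpha 0.142.
- Alpha is below 0.06 in 21 combinations and above 0.10 in 1.

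With centres as the clusters, m can be much larger. For 8 centres, m = 965/8 = 120.6. At ICCs of 0.05 and 0.10, DE = 1 + 119.6 × 0.005 = 1.60, so the shortfall is 21% and alpha 0.121. With ICC(risk) = 0, DE = 1 for any m.

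The formula was checked by simulation. For 20 clusters and both ICCs 0.05 it gives a true-to-model SE ratio of 1.057; the simulation gave 1.055.

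**Confounding.** With correlation ρ between the cluster effects on risk and on change, the spurious slope is ρ√(ICC(risk) × ICC(change)). At ICCs of 0.05 and 0.10 this is 0.0071 for ρ = 0.1 and 0.0141 for ρ = 0.2. The model SE is 1/√965 = 0.0322, so these are 0.22 and 0.44 standard errors.

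The simulation used 965 patients, 48 doctors, 8 centres, the same ICCs, change as outcome, no true effect, no covariates and 4000 runs per cell. Rejection rates without cluster terms are listed for cluster variance at doctor level / split / centre level:

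| ρ | Continuous risk | Four categories |
|---|---|---|
| 0 | 0.057 / 0.071 / 0.111 | 0.055 / 0.061 / 0.082 |
| 0.1 | 0.072 / 0.076 / 0.116 | 0.058 / 0.063 / 0.078 |
| 0.2 | 0.087 / 0.095 / 0.123 | 0.069 / 0.072 / 0.085 |

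The part due to confounding is the difference from the ρ = 0 row.

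- Continuous risk: 0.015 / 0.005 / 0.005 at ρ = 0.1, and 0.030 / 0.024 / 0.012 at ρ = 0.2.
- Four categories: 0.003 / 0.002 / −0.004, and 0.014 / 0.011 / 0.003.

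Simulation error is about 0.004 to 0.005 per rate. At ρ = 0.3 the continuous rates are 0.112 / 0.123 / 0.155, an addition of 0.055 / 0.052 / 0.044.

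**Sensitivity to the ICCs** (split case, continuous risk, 3000 runs, ρ = 0.1 / 0.2 / 0.3). If covariates absorb half of both cluster variances, the rates are 0.052 / 0.060 / 0.058. At ICCs of 0.10 and 0.20 they are 0.158 / 0.210 / 0.290.

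**The remedy** (continuous risk only; doctor / split / centre level). Centre fixed effects with doctor-robust errors give 0.050 / 0.051 / 0.058 at ρ = 0, 0.069 / 0.057 / 0.047 at ρ = 0.2 and 0.085 / 0.064 / 0.053 at ρ = 0.3. Adding the doctor's mean risk gives 0.045 to 0.054 in all nine cells for ρ = 0.1 to 0.3.

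**The case against.** The strongest reply is that the analysis section is a short outline. It gives no model equation, random-effects structure or covariate list, so a centre term is unspecified, not ruled out. That is fair, and the point is limited to models fitted as specified. But the outline does say which correlation the mixed models handle and what kind of covariate enters, and neither description reaches doctor or centre.

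It can also be said that every input except 965 is assumed, that the covariates may absorb cluster differences, and that risk may hardly cluster. All of this stands. Under such conditions the inflation is close to nil, and the plan may lose nothing by its omission.

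A reader might go further and infer that centre or doctor confounding will distort the association, or read the centre-level rejection rate of 0.123 at ρ = 0.2 as its effect. The documents do not support this. They report no centre differences in change, and 0.111 of that 0.123 is already present at zero correlation. Doctors record blood pressure and cholesterol but interviewers give the cognitive tests, so a doctor's measuring habits do not directly affect the outcome. How interviewers were allocated to centres is not stated. Nor does the ordinary cluster design effect, 1 + (m − 1) × ICC, apply, because risk varies between patients within a cluster.

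Finally, the remedy is partial: centre terms do not remove confounding at doctor level. That also stands and shapes the fix.

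**Conclusion.** The omission is real and its consequence is conditional. If risk and 5-year change both cluster by doctor or centre, standard errors from the models as specified are too small. The loss is typically a few percent for small clusters and may be about a fifth for a handful of large centres. Neither size is established, because the documents give no numbers of doctors or centres and no ICCs.

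Confounding by centre or doctor remains possible but unshown. At assumed correlations of 0.1 to 0.2 and ICCs of 0.05 and 0.10 it adds about 0 to 0.03 to the rejection rate, and less with risk in the four planned categories. This is a minor point, with low confidence in the magnitude. It is worth acting on because the better analysis is cheap.

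**What to change.** In the regression, covariance and mixed models that address the primary objective, for each test:

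- Add health centre as a fixed effect, with centre × time where repeated scores are modelled.
- Use doctor-level cluster-robust standard errors with a small-cluster correction.
- Report the numbers of doctors and centres.
- As a sensitivity analysis, add the doctor's mean risk as a covariate. Do not claim that centre terms remove all clustering bias.

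The cost is some SAP wording, a few degrees of freedom and slightly wider intervals. In the simulation at ICCs of 0.05 and 0.10, the standard error is about 2% above that of the model without cluster terms. With the doctor's mean risk added it is about 5% above with 48 doctors and 8% to 9% above with 97. Table 1 lists no doctor or centre identifier, so the sponsor must first confirm that both can be recovered from the sampling lists.

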### Patient selection criteria.

1. Inclusion criteria:
  - a. Age 55 to 74 years
  - b. Agreeing to participate and provide written informed consent
  - c. Having completed the neuropsychological assessment of the NEDICES-2 study
2. Exclusion criteria:
  - a. To have dementia at the beginning of the study

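### Patients with prior coronary disease or stroke are classified by a score that predicts such events, and the analysis plan has no rule for them

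*Combined protocol and SAP*

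**What the plan says.** Under Patient selection criteria there is one exclusion: "To have dementia at the beginning of the study". The inclusion criteria are an age range, consent and "Having completed the neuropsychological assessment of the NEDICES-2 study"; none asks for freedom from cardiovascular disease. The Methods / Design section describes a random sample of primary care users, stratified by sex and age, "in which the presence of dementia in the initial neuropsychological evaluation was ruled out". Nothing else is ruled out.

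The primary objective is the association between "cardiovascular risk, calculated with the Framingham REGICOR and FRESCO risk functions, and the cognitive decline after 5 years of follow-up". Statistical Analysis enters baseline risk in four categories, with one mixed model per test. It gives no cut-points and says nothing about patients with earlier events. Adjustment is for sociodemographic and clinical variables that are not listed.

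The footnote to Table 1 (Procedure) expands the second score as "FRESCO: Función de Riesgo Española de acontecimientos Coronarios y Otros", a risk function for coronary and other events. The opening section discusses cardiovascular risk in terms of how often events occur in Spain: "the incidence of coronary heart disease and stroke are lower than expected taking into account the cardiovascular risk factors". Table 1 shows that morbidity is collected at baseline, but no rule in the plan uses it to separate patients with prior events.

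**The concern.** A predicted risk of an event is a natural exposure for people who have not had the event. For someone who has had it, the number may say little about vascular burden. Such a patient could score low or high, and may also decline faster for reasons that the score does not capture.

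If these patients sit mainly in the lower categories, faster decline there narrows the gap between top and bottom. If they sit mainly in the top category, part of the gap may come from past disease and not from calculated risk. The second case bears on the study's stated purpose, which is to find people at risk of cognitive decline by means of predictive vascular models. An association carried by past stroke would not show that the score does this. The reliable-change analysis in high-risk subjects uses the same classification.

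**Working it through.** **The plan's own figure.** The sample size of 965 is given without power, effect size, SD or dropout, so it cannot be reproduced. The point does not depend on it.

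**Inputs.** From the documents: N = 965, four categories, significance at p < 0.05. Assumed, because the documents give no value: prevalence p of prior coronary disease or stroke of 5%, 10% or 15%; disease-free category means of 0, -0.067, -0.133 and -0.20 SD in four equal groups; mean change of -0.5 SD in patients with prior disease, whatever their category; no covariate adjustment.

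**Step 1: bounding placements.** Each category holds (1 - p)/4 disease-free patients, as a share of the cohort, plus the prior-disease patients placed there. At p = 10% the disease-free share is 0.225 per category.

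- All prior disease in the lower half, 0.05 in each of the two bottom categories. Bottom mean = -0.5 × 0.05/0.275 = -0.091. Contrast = -0.20 + 0.091 = -0.109.
- All prior disease in the top category. Fraction = 0.10/0.325 = 0.308. Top mean = -0.20 × 0.692 - 0.5 × 0.308 = -0.292. Contrast = -0.292.

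| Prior disease | All in lower half | Disease-free value | All in top category |
|---|---|---|---|
| 5% | -0.152 | -0.20 | -0.252 |
| 10% | -0.109 | -0.20 | -0.292 |
| 15% | -0.070 | -0.20 | -0.324 |

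**Step 2: intermediate placements at 10%.**

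- Even spread: bottom -0.05, top -0.9 × 0.20 - 0.1 × 0.5 = -0.23, contrast -0.18.
- 15/20/30/35% from bottom to top: bottom -0.5 × 0.015/0.240 = -0.031; top fraction 0.035/0.260 = 0.135, top mean -0.240; contrast -0.21.
- The reverse split: bottom -0.067, top -0.219, contrast -0.15.

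The shifts from -0.20 are at most 0.05 SD. The standard error of a top-versus-bottom contrast with 965 patients in equal quarters and unit SD is sqrt(2/241.25) = 0.091 SD, so these shifts are about half a standard error or less.

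**Step 3: a second model.** A simulation with 400,000 patients used a slope of -0.10 SD per SD of risk, quartile categories and 0.5 SD extra decline in patients with prior disease. Their recorded score was shifted relative to their underlying risk. The entries are the full-cohort contrast divided by the disease-free contrast.

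| Score shift (SD) | 5% | 10% | 15% |
|---|---|---|---|
| -1 | 0.753 | 0.539 | 0.367 |
| -0.5 | 0.873 | 0.760 | 0.675 |
| 0 | 1.004 | 0.989 | 1.008 |
| +0.5 | 1.124 | 1.227 | 1.301 |
| +1 | 1.211 | 1.363 | 1.503 |

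With no shift there is no distortion. Here patients with prior disease keep the risk gradient, whereas in Step 1 they all have the same mean; that is why an even spread dilutes the contrast in Step 2 but not here.

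**Step 4: confounding alone.** Shift = -d × [P(prior | top) - P(prior | bottom)]. With 20% in the top category and 3% in the bottom, d = 0.3 gives -0.051 SD and d = 0.5 gives -0.085 SD. The reverse pattern gives the same sizes with positive sign.

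**Step 5: price of an event-free model.** The standard-error factor is 1/sqrt(1 - p): 1.026, 1.054 and 1.085 for 5%, 10% and 15%. About 917, 869 or 820 patients remain. At two-sided 0.05 and 80% power (assumed), the detectable top-versus-bottom difference is 2.80 × sqrt(2/(n/4)). It is 0.255 SD for 965, and 0.262, 0.269 and 0.277 SD for the reduced sets.

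**The case against.** Several objections have force.

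A reader might infer that these patients *are* misassigned, or that treatment after an event lowers blood pressure and cholesterol and so moves them into a low category. The documents support neither. They give no cut-points, do not say in which population the functions are valid, and never state what enters either function or how treatment is handled. What is documented is that the patients are included and that no rule covers them. The opening section's remark on Spanish incidence is epidemiology and does not define the scores' output; the expanded name of FRESCO is the firmer support.

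The plan adjusts for clinical variables, and prior disease could be among them. That would reduce confounding by past stroke. It would not make the category a better description of these patients, and the list is not given.

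The wide range needs every patient with prior disease to fall at one end. Intermediate placements move the contrast little, and scores distributed like those of other patients leave it unchanged in the simulation.

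A deficit already present at baseline does not bias a contrast in decline. Only extra decline after baseline does so, and its size is assumed.

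Finally, the primary objective names the whole cohort. Making the event-free subset the only primary set would narrow that target, and clinical events may lie on the pathway from risk to decline. This stands, so either order of the two analyses is acceptable if it is fixed in advance.

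**Conclusion.** The omission is certain on the text; its effect is possible but not measured. Patients with prior coronary disease or stroke are eligible, are scored like everyone else, and may sit in categories that do not reflect their burden. The association with decline can then be too weak or too strong. The documents give neither the prevalence nor the extra decline, so the size is unknown. The -0.11 to -0.29 SD at 10% prevalence, against -0.20 SD in disease-free patients, is a bounding case without adjustment and with every input assumed. It is not an estimate of the bias in this cohort.

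A reader might go further and infer that any association found would be due to past stroke, or that the primary result is invalid. The documents support neither reading. They show that the plan as written could not tell these explanations apart. Because a rule costs little and uses data already listed for collection, it is worth adding.

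**What to change.** In Statistical Analysis, define prior coronary disease and prior stroke from the baseline morbidity record. Prespecify the REGICOR and FRESCO models in two forms: in patients free of these events, and in the full cohort with prior disease as a separate fifth category. State in advance which is primary. Conclude that calculated risk predicts decline only if the finding holds in the event-free analysis. Nobody leaves the cohort or the secondary objectives.

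The cost is wording, plus standard errors about 3-8% larger in the event-free model if 5-15% have prior disease. No new data are needed, provided that the morbidity record identifies coronary disease and stroke; Table 1 gives no item list, so this should be confirmed first. With baseline in 2014-2017 and five years of follow-up, assessments fall due in 2019-2022. At the document date of July 2019 the rule could still be set before most outcomes were known.
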